7.2. Treatment Assignment and Blinding

7.2.1. Treatment Assignment

After successfully meeting study entry criteria, subjects will be randomly assigned in a 1:1 ratio to 1 of the following treatments:

- 2 mg/day dasotraline (N = 50 subjects)
- Placebo (N = 50 subjects)

An Interactive Response System (IXRS) will be used to manage randomization on Day 1 and, if necessary, for emergency unblinding (see [Section 7.2.3](#)) of treatment assignment during the study. The IXRS is an integrated web based subject and drug management system.

Study medication will be assigned by an IXRS based on the randomization schedule. The IXRS will generate instructions on which medication number to assign to a subject.

7.2.2. Blinding

This is a double-blind study. All study drug capsules (both dasotraline and placebo) are identical in color, shape, size, and packaging in order to maintain the blind.

Subjects, Sponsor personnel, Investigator staff, persons performing the assessments, clinical operations personnel, data analysts, and personnel at central laboratories will remain blind to the identity of the treatment from the time of randomization until database lock and unblinding, using the following methods; (1) randomization data are kept strictly confidential until the time of unblinding, and will not be accessible by anyone else involved in the study with the exception of Data and Safety Monitoring Board (DSMB) members involved in regular review of safety data, and Clinical Trial Materials Management personnel, (2) the identity of the treatments will be concealed by the use of study drugs that are all identical in packaging, labeling, schedule of administration, and appearance.

7.2.3. Emergency Unblinding Procedures

The IXRS will be used, if necessary, for emergency unblinding of treatment assignment during the study. The blinded dose information is to be broken only in an emergency when knowledge of such treatment may have an impact on further treatment decisions or aid in the emergency treatment of the subject. Any subject for whom the blind is broken is to be discontinued from receiving any additional study drug and should undergo early termination procedures as described in [Section 14](#).

7.3. Rationale

7.3.1. Rationale for the Study Design

The current study is a randomized, double-blind, placebo-controlled, parallel-group, laboratory classroom study in pediatric subjects with ADHD weighing ≤ 30 kg. This study was designed to evaluate the efficacy and duration of effect of dasotraline (2 mg/day) compared with placebo over an entire day in a simulated classroom setting. The laboratory school protocol is a particularly useful method for evaluation of efficacy in subjects with ADHD because it

represents a controlled study setting for evaluation and comparison of study treatments and is designed to mimic a typical school day.

7.3.2. Rationale for the Dosages

The dosage of 2 mg/day of dasotraline was selected to evaluate dasotraline safety, tolerability, and efficacy within the dose range being evaluated in the ongoing studies in pediatric subjects with ADHD.

A dasotraline 2 mg/day dose is expected to produce mg/kg exposures in pediatric subjects weighing ≤ 30 kg similar to those demonstrated to be effective in both children and adults with ADHD. In prior studies it was noted that AEs appear to be dose related. Therefore, 2 mg in smaller children may be efficacious and better tolerated.

7.3.3. Rationale for the Study Population

The subject population includes males and females ranging from 6 to 12 years of age, and in concert with standard practice guidelines, will be required to have a diagnosis of ADHD established by a comprehensive psychiatric evaluation that reviewed Diagnostic and Statistical Manual for Mental Disorders, Fifth Edition (DSM-5) criteria for ADHD (inattentive, hyperactive, or combined presentation); diagnosis will be confirmed using the Schedule for Affective Disorders and Schizophrenia for School-Age Children Present and Lifetime Version (K-SADS-PL). Subjects are required to weigh ≤ 30 kg since a 2 mg/day dose in such a group is expected to have mg/kg exposures similar to those demonstrated to be effective in children and adults.

7.3.4. Rationale for the Endpoints

The primary efficacy measure (mean SKAMP-Combined Score) is a widely accepted efficacy endpoint intended to assess functional impairment related to ADHD and has been used in many laboratory classroom studies in children ([Childress-2015](#), [Wigal-2014](#)).

7.4. Prevention of Missing Data

In an effort to minimize the number of subjects who are terminated from the study prior to study completion, the following study design and conduct elements are implemented; (i) use of clinical sites with a good track record of having performed this type of study, (ii) training provided to the clinical sites on the importance of the informed consent/assent process and ensuring subjects and their parent/guardian understand the commitment they are making, including the intent to complete the trial, and (iii) monitoring data collection for adherence during the study.

8. SELECTION OF SUBJECTS

Subjects may be rescreened a maximum of 2 times for out of range clinical laboratory results, insufficient medication washout periods, etc.

8.1. Subject Inclusion Criteria

The subjects who fulfill the following criteria will be included in the study.

1. Subject is 6 - 12 years old, inclusive at screening and randomization.
2. Subject weighs ≤ 30 kg at the time of screening.
3. At least one of the subject's parents/legal guardians must give written informed consent, including privacy authorization, prior to study participation. The subject will provide informed assent prior to study participation.
4. Subject meets Diagnostic and Statistical Manual of Mental Disorders Fifth Edition (DSM-5) criteria for a primary diagnosis of ADHD (inattentive, hyperactive, or combined presentation) at screening established by a comprehensive psychiatric evaluation that reviews DSM-5 criteria and confirmed using the Schedule for Affective Disorders and Schizophrenia for School-Age Children-Present and Lifetime version (K-SADS-PL) at screening.
5. Subject is currently either untreated for ADHD or receiving a treatment regimen of a stimulant medication prescribed as monotherapy (i.e., methylphenidate, mixed amphetamine salts, lisdexamphetamine, or dextroamphetamine) within the approved labeled dose range for ADHD.
6. In the opinion of the investigator, the subject is not treatment refractory.
7. Any subject not receiving ADHD medication at screening must display clinically significant ADHD symptoms, as measured by an ADHD-RS-IV score ≥ 26 at screening and Day -7.
8. For any subject receiving monotherapy stimulant treatment for ADHD, that treatment must be well tolerated and clinically effective based on clinical assessment and informant interview, as well as, review of available medical records. Note: The ADHD Rating Scale Version IV - Home Version (modified for investigator administration) (ADHD-RS-IV HV) will be administered at Screening by the investigator to inform clinical evaluation.
9. Subject is male or a non-pregnant, non-lactating female.
10. Subject, if female, must not be pregnant or breastfeeding, and if ≥ 8 years of age must have a negative serum pregnancy test at screening.
11. Female subjects of childbearing potential and male subjects with female partners of childbearing potential must practice true abstinence (consistent with lifestyle) and must agree to remain abstinent or agree to use an effective and medically acceptable form of birth control, from the time of informed consent/assent to at least 14 days after the last dose of the study drug has been taken. See [Section 10.5](#) for information on acceptable methods of birth control.

12. Subject must be in general good health (defined as the absence of any clinically relevant abnormalities as determined by the investigator) based on screening physical and neurological examinations, medical history, and clinical laboratory values (hematology, chemistry, and urinalysis). Note: If any of the hematology, chemistry, or urinalysis results are not within the laboratory's reference range, then the subject can be included only if the investigator determines the deviations to be not clinically relevant.
13. Subject is within the 3rd to 97th percentile for gender specific weight-for-age from the Centers for Disease Control and Prevention (CDC) growth charts. See [Sections 24](#), and [25](#), Appendix V and VI for growth charts.
14. Subject must report a history of being able to swallow capsules.
15. Subject and subject's parent/legal guardian must be able to fully comprehend the informed consent/assent forms, understand and be willing and able to comply with all study procedures and visit schedule, and be able to communicate satisfactorily with the investigator and study coordinator.
16. Subject, on Day -1, has evidence of clinically significant ADHD symptoms as measured by an ADHD-RS-IV HV total score ≥ 26 . If subject has been receiving stimulant pharmacotherapy for ADHD the ADHD-RS-IV should be administered following a minimum 72-hour washout from prior ADHD medication treatment.

8.2. Subject Exclusion Criteria

The subjects who meet any of the following criteria will be excluded from the study

1. Subject or parent/legal guardian has commitments during the study that would interfere with attending study visits.
2. Subject is currently being treated for ADHD with a non-stimulant product, or has been treated with a non-stimulant product in the 4 weeks prior to the start of screening.
3. Subject has failed 2 adequate courses (dose and duration) of stimulant or non-stimulant treatment for ADHD.
4. Subject is considered treatment refractory, as judged by the investigator.
5. Subject currently has a diagnosis of asthma that has required daily treatment with bronchodilators or nebulizer treatments in the 30 days prior to screening and/or who may require daily treatments with these agents over the course of the trial. Intermittent use of bronchodilators is not exclusionary. Subjects who have a history of requiring persistent asthma treatment should be discussed with the medical monitor prior to randomization.
6. Subject has any clinically significant unstable medical abnormality, chronic disease, or a history of a clinically significant abnormality of the cardiovascular, gastrointestinal, respiratory, hepatic, or renal systems, or a disorder or history of a condition (eg, malabsorption, gastrointestinal surgery) that may interfere with drug absorption, distribution, metabolism, or excretion. Note: Active medical conditions that are minor or well-controlled are not exclusionary if they do not affect risk to the subject or the study results. In cases in which the impact of the condition upon risk to the subject or study results is unclear, the medical monitor should be consulted. Any subject with a known

cardiovascular disease or condition (even if controlled) must be discussed with the medical monitor during screening.

7. Subject has a history or presence of abnormal ECGs, which in the investigator's opinion is clinically significant. Screening site ECGs will be centrally over-read, and eligibility will be determined by the investigator based on the results of the over-read report.
8. Subject has any diagnosis of bipolar I or II disorder, major depressive disorder, conduct disorder, obsessive-compulsive disorder, any history of psychosis, autism spectrum disorder, disruptive mood dysregulation disorder (DMDD), intellectual disability, Tourette's Syndrome, confirmed genetic disorder with cognitive and/or behavioral disturbances. Note: Subjects with oppositional defiant disorder (ODD) are permitted to enroll in the study as long as ODD is not the primary focus of treatment.
9. Subject has a first-degree relative (biological parent or sibling) with a history of schizophrenia, schizoaffective disorder, bipolar I disorder, or bipolar II disorder.
10. Subject has generalized anxiety disorder or panic disorder that has been the primary focus of treatment at any time during the 12 months prior to screening or that has required pharmacotherapy any time during the 6 months prior to screening.
11. Subject has evidence of any chronic disease of the central nervous system (CNS) such as tumors, inflammation, seizure disorder, vascular disorder, potential CNS related disorders that might occur in childhood (eg, Duchenne Muscular dystrophy, myasthenia gravis, or other neurologic or serious neuromuscular disorders).
12. Subjects with a history of persistent neurological symptoms attributable to serious head injury.
13. History of febrile seizure, drug-induced seizure, or alcohol withdrawal seizure is exclusionary.
14. Subjects taking anticonvulsants for seizure control currently or within the past 2 years are not eligible for study participation.
15. Subject has uncontrolled thyroid disorder as evidenced by thyroid stimulating hormone (TSH) ≤ 0.8 x the lower limit of normal (LLN) or ≥ 1.25 x the upper limit of normal (ULN) for the reference laboratory.
16. Subject answers "yes" to "Suicidal Ideation" item 4 (active suicidal ideation with some intent to act, without specific plan) or item 5 (active suicidal ideation with specific plan and intent) for any lifetime history on the C-SSRS Children's Lifetime/Recent assessment at screening.
17. Subject has any history of attempted suicide or clinically significant suicidal ideation, in the opinion of the investigator.
18. Subject has a history of severe allergies to more than 1 class of medication or multiple adverse drug reactions or has a history of allergic reaction or has a known or suspected sensitivity to any substance that is contained in the study drug formulations.
19. Subject has history of intolerance (safety) or lack of efficacy to stimulants.
20. Subject has taken any antipsychotic medication within 6 months prior to screening.

21. Subject has taken any herbal and/or complementary treatments, eg, St. John's Wort, within 6 months prior to Day 1.
22. Subject has taken any antidepressant medication (eg, bupropion, selective serotonin reuptake inhibitor [SSRI]/ serotonin norepinephrine reuptake inhibitor [SNRI], tricyclic, etc) within 6 months prior to Day 1.
23. Subject has ever taken any monoamine oxidase [MAO] inhibitor at any time.
24. Subject is currently undergoing ongoing or newly initiated Cognitive Behavioral Therapy (CBT) for the treatment of ADHD; behavioral therapies, including school based interventions that were initiated less than one month prior to screening; or, behavioral therapy that in the opinion of the investigator would interfere with the subject's ability to participate for the duration of the study. School based interventions that have been in place for more than one month prior to screening will be allowed. Note: Unavoidable changes in school-based interventions that occur during study participation will not be exclusionary, but should be documented by the investigator, to the extent possible. Subjects should not be enrolled who, in the judgment of the investigator, are expected to start substantially different or more intensive course of behavioral therapy over the duration of their participation in the study.
25. Subject or subject's family anticipates a move outside the geographic range of investigative site during the study period, or plans extended travel inconsistent with the recommended visit interval during study duration.
26. Subject has history of, or current, malignancy other than non-melanomatous skin cancer.
27. Subject has history of positive test for Hepatitis B surface antigen or Hepatitis C antibody.
28. Subject is known to have tested positive for human immunodeficiency virus (HIV).
29. Subject has participated in a classroom study within 6 months prior to the start of screening or has participated in any other clinical study with an investigational drug/product within 90 days prior to the start of screening or is currently participating in another clinical trial.
30. Subject shows evidence of substance or alcohol use or is currently using tobacco or other nicotine-containing products, or has a positive urine drug screen (UDS) at screening. Note: Subjects with a positive UDS may be allowed to continue in the study, provided that the investigator determines that the positive test is as a result of taking medications as prescribed after consultation with the medical monitor.
31. Subject is taking any disallowed medications for chronic treatment.
32. Subject has previously been enrolled in a clinical trial of dasotraline (SEP-225289).
33. Subject's parent/legal guardian is an investigational site staff member or the relative of an investigational site staff member.
34. Subject is, in the opinion of the investigator, unsuitable in any other way to participate in this study.

35. Subject's sibling or family member living in the same household is participating in the same laboratory classroom cohort for this study.
36. Subject is unable to perform at the basic level of the standardized math test as defined in the laboratory classroom manual.

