11.5.2. Double-blind Period

11.5.2.1. Visit 4 (Day 1): First Laboratory Classroom Day

At this visit the subject should arrive at the clinic by 6:30 AM and the following study-related procedures will be performed:

- Record prior and concomitant medications
- Review inclusion/exclusion criteria
- Measure weight, record BMI
- Collect vital signs once.
- Administer C-SSRS since last visit version
- Collect samples for UDS, urine pregnancy test for females ≥ 8 years of age
- Randomize to treatment
- Dispense study drug
- Provide dosing diary
- Conduct 7 classroom sessions according to a Laboratory Classroom Manual common to all investigational sites.

Subjects will begin taking double-blind study drug on the evening of Day 1 at approximately 8 PM plus or minus 30 minutes. The first dose of study drug may be administered in the clinic, after all assessments are completed, or at home.

During the double-blind period, the clinical site will attempt to contact the subject's parent/legal guardian daily with a reminder to administer study drug.

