22. APPENDIX III. CLINICAL LABORATORY TESTS

The following clinical laboratory tests are to be performed.

Clinical Safety Panel

HEMATOLOGY: (Differential reported as % and absolute value)
Hemoglobin, Hematocrit, Platelet Count, RBC Count, WBC - Total Count, WBC Differential, (Basophils, Eosinophils, Lymphocytes, Monocytes, Neutrophils)

BLOOD CHEMISTRIES: Alanine aminotransferase (ALT), Alkaline Phosphatase (ALP), Aspartate aminotransferase (AST), Bicarbonate (HCO₃), Bilirubin (Total, Direct, Indirect), Blood Urea Nitrogen (BUN), Calcium (Ca), Chloride (Cl), Creatinine, Glucose, Magnesium (Mg), Phosphorus (P), Potassium (K), Protein (Total), Sodium (Na), Uric Acid, Albumin

URINALYSIS: Blood, Glucose, Ketones, Leukocyte esterase, Microscopic examination, Nitrites, pH, Protein

THYROID PANEL: Thyroid stimulating hormone (TSH)

URINE DRUG SCREENING: Amphetamines, Barbiturates, Benzodiazepines, Cannabinoids, Cocaine, Cotinine, Methamphetamines, Methadone, Methylenedioxymethamphetamine (MDMA), Phencyclidine (PCP), Opiates, Oxycodone

OTHER TESTS: Serum Pregnancy (β -HcG) (in female subjects only ≥ 8 years of age), Urine Pregnancy Test (in female subjects only ≥ 8 years of age)

Laboratory reports will be initialed and dated on all pages by the Investigator listed on the Form FDA 1572 (MD or DO). Laboratory test results will be reviewed by the Investigator as they become available. The Investigator must determine the clinical significance of all out-of-range lab values (except drug screens). Possibly drug-related or clinically relevant abnormal values of uncertain causality must be repeated. Any abnormal values that persist should be followed at the discretion of the Investigator.

[figure not shown]
23. APPENDIX IV. CLINICALLY RELEVANT CYP2B6 SUBSTRATES OR INDUCERS OR INHIBITORS (GENERIC NAMES)

The following drugs are prohibited during this study.

Substrate	Inhibitor	Inducer
artemisinin	clopidogrel	artemisinin
bupropion	thiotepa	carbamazepine
cyclophosphamide	ticlopidine	efavirenz
efavirenz	voriconazole	nevirapine
ifosfamide		phenobarbital
Ketamine		phenytoin
meperidine		rifampin
methadone		
nevirapine		
Propafol		
Selegiline		
sorafenib		

Flockhart DA. Drug Interactions: Cytochrome P450 Drug Interaction Table. Indiana University School of Medicine (2007). <http://medicine.iupui.edu/clinpharm/ddis/table.aspx>. Accessed 4 March 2016.

24. APPENDIX V. GROWTH CHART (MALE).

[figure not shown]

25. APPENDIX VI. GROWTH CHART (FEMALE).

2 to 20 years: Girls

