#### 4.5 Protocol Deviations

Protocol deviations (PDs) will be collected during monitoring visits. Protocol deviations will be placed into, but not limited to, the following categories: prohibited concomitant medications, dosing, enrollment inclusion/exclusion criteria, laboratory, non-compliance, and others which are deemed to be study PDs. Each instance of a PD will be reviewed and determined to be important or minor before the study DBL.

A summary of important PDs will be provided as number (%) of subjects with at least 1 important PD and number (%) of subjects in each category in all randomized subjects. A listing by subject will also be provided that will include all PDs, deviation date, type, and any specific comments related to the deviation.

The following conditions, if met, would constitute an important PD. As such, any subject meeting one or more of these conditions would be omitted from the PP population. Important PDs are not limited to the list below. All protocol deviations within the monitoring report and the clinical database will be reconciled and adjudicated by the clinical team after the study is complete for the identification of all other important PDs.

	Category	Explanation
1	No proof of randomization or subjects mistakenly randomized	At Visit 4, there is no randomization number indicated on CRF field or subject mistakenly assigned randomization number.
2	Subject is non-compliant	Subject is not lost to follow-up and is <75% or >125% compliant with study drug.
3	Prohibited medications taken	Subject took any of the prohibited medications listed in Section 10.3.1 of the protocol during the study from screening through the EOS visit, unless the medication is clinically adjudicated as permissible.

4	Treated subject who did not meet inclusion/exclusion criteria	Subject failed one or more of the inclusion or exclusion criteria listed in Section 8 of the protocol, but continued in the double-blind period of the study.
5	Subject tests positive for substance abuse	Subject has one or more positive urine drug screen test at any visit during the course of the study.
6	Subject is unblinded during study	Subject is unblinded to treatment at any time during the course of the study.
7	Subject receives incorrect treatment	Subject's actual treatment received does not match randomized planned treatment.
8	Subject misses Day 15 visit	Subject is randomized and receives treatment, but is not present for the Day 15 classroom assessments

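### Exclusion 30 gives no rule for the Day 1 urine drug screen, while SAP deviation rule 5 removes from the per-protocol set any child with a positive at any visit, including a screening positive that the protocol accepts

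*Protocol*

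**What the plan says.** **Eligibility.** Protocol 8.2, exclusion 30, has two parts. The first is general: "Subject shows evidence of substance or alcohol use or is currently using tobacco or other nicotine-containing products". The second concerns the test and names one visit: "or has a positive urine drug screen (UDS) at screening". A note then softens it: "Subjects with a positive UDS may be allowed to continue in the study", provided the investigator, after consulting the medical monitor, attributes the result to medication taken as prescribed. The note names no visit.

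**Day 1.** Protocol 11.5.2.1 includes "Collect samples for UDS, urine pregnancy test for females ≥ 8 years of age" and lists this ahead of randomisation, with a review of the eligibility criteria on the same day. Table 2 schedules the drug screen at Visit 1, Day 1, Day 15 and end of study, and at neither Day -7 nor Day -1.

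**Analysis.** Rule 5 of SAP 4.5 counts as an important deviation: "Subject has one or more positive urine drug screen test at any visit during the course of the study". A child meeting any listed condition is left out of the per-protocol population. The primary analysis is on the ITT population (SAP 7.5.1), with the per-protocol analysis as a supplement (SAP 4.3).

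**The concern.** The eligibility rule and the deviation rule use the same test but cover different visits. On Day 1 the site holds a sample that bears directly on whether the baseline classroom is valid, and the protocol does not say what to do with the result. The baseline mean SKAMP-Combined score is both the reference for the change score and the covariate in the ANCOVA. If a child attends the baseline classroom with a stimulant on board, both are mis-measured for that child. The trial would also be randomising a child it could already identify as a per-protocol exclusion.

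The mismatch runs the other way too. The protocol accepts some screening positives, and the SAP then treats those same children as important deviators.

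**Working it through.** The point is a comparison of texts. Arithmetic serves only to size it.

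**1. Can the screening test check washout?** No. Visit 1 falls no later than Day -8. Washout lasts 3 to 5 days before Day -1, so it starts no earlier than Day -1 minus 5 = Day -6. The screening sample always precedes it. The Day -1 contact is by telephone. The Day 1 sample is the only scheduled objective check before the baseline classroom.

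**2. Does another criterion catch a dose given after the Day -1 call?**
- Inclusion 16 is judged on Day -1 and has already been passed.
- The general part of exclusion 30 (substance use) does not plainly reach a child's own prescribed stimulant.
- The note to exclusion 30 has no visit limit. Read on Day 1, it offers a route to accept the positive.
- Exclusion 31 is confined to disallowed medication taken as chronic treatment.
- Exclusion 34 is general investigator discretion.
- Protocol 7.1 and 10.3.1 tie the 72-hour washout to the Day -1 assessment. One sentence of the synopsis ties it to Day 1. These need reconciling.

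No criterion names the Day 1 result.

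**3. What does the SAP do with that child?** Rule 5 applies as worded and the child leaves the per-protocol set. Rule 3 (prohibited medication) refers to Protocol 10.3.1, whose during-study list names non-stimulant agents where the synopsis names stimulant agents. Those lists also need reconciling, so rule 3 is not a clear substitute.

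**4. What does the SAP do with an accepted screening positive?** Inclusion 5 admits children on amphetamine products, and by step 1 they may still be taking them at Visit 1. The Appendix III panel includes amphetamines: "URINE DRUG SCREENING: Amphetamines, Barbiturates, Benzodiazepines, Cannabinoids, Cocaine, Cotinine, Methamphetamines, Methadone", among others. Such a child can be enrolled under the note. Rule 3 carries an exception for clinically adjudicated cases; rule 5 carries none. The later adjudication described in SAP 4.5 is there to identify further important deviations, not to release listed ones.

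**5. Size.** First the plan's own figure: two-sample t-test, effect size d = 0.7, two-sided alpha 0.05, n = 44 per arm. The noncentrality is d × √(n/2) = 0.7 × √22 = 3.28 on 86 degrees of freedom, giving power 0.901. The solved n is 43.9, rounded up to 44. With 12% dropout, 88 / 0.88 = 100. Both agree with the documents.

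Now suppose that all 88 completers would otherwise be in the per-protocol set and that k of them are removed:

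| k removed | per arm | power |
|---|---|---|
| 0 | 44 | 0.901 |
| 2 | 43 | 0.894 |
| 4 | 42 | 0.887 |
| 8 | 40 | 0.871 |

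For the ITT analysis, I simulated the ANCOVA without a site term: 44 per arm, a true effect of 0.7 residual SD, the observed baseline lowered by 1 SD in 5% of children irrespective of arm, and an assumed correlation between baseline and Day 15 of 0.5 or 0.7. The mean estimate stayed at 0.70. Power moved from about 0.90 to no lower than 0.88 to 0.89.

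**The case against.** The strongest reply is that nothing in the protocol permits randomising such a child. ADHD medication is prohibited during washout, concomitant medication is reviewed on Day 1, the eligibility criteria are reviewed again that day, exclusion 34 is available, and insufficient washout is already a ground for re-screening. This stands in part. What is missing is an explicit rule, and a careful site could still stop the child. But the remaining routes rest on parental report or discretion, so sites can differ, and the note to exclusion 30 can point the other way.

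A second reply is that the result may not be available in time. That the sample precedes randomisation rests on the order of a list, and Protocol 11.4.2 says laboratory tests are done centrally. Against that, the same section provides for on-site kits, and Table 7 codes the drug screen like the urine pregnancy test, not like the central laboratory tests. Same-morning availability is plausible but not stated.

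A third reply is that rule 5 is headed as substance abuse and so may not be meant for prescribed medication. That is a fair reading of the heading, but the condition itself is unqualified.

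Two wider readings are tempting and not supported:
- **The C-SSRS.** A reader might infer the same gap there, because exclusion 16 applies "for any lifetime history on the C-SSRS Children's Lifetime/Recent assessment at screening" and a later version of the scale is given on Day 1. But exclusion 17 covers attempted suicide and clinically significant ideation without a visit limit and can be applied at the Day 1 review. Rule 5 concerns urine drug screens only.
- **Methylphenidate.** A reader might infer that the panel misses it because it is not named. That depends on assay details that the documents do not give.

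**Conclusion.** The gap is real and worth closing, but modest. Exclusion 30 is silent on a Day 1 positive, and rule 5 conflicts with the note to exclusion 30.

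A reader might infer that a contaminated baseline biases the treatment comparison. It does not: the Day 1 result arises before randomisation and treatment is blinded, so it is unrelated to arm. ITT membership is also unchanged. The effect is extra noise in the primary analysis and loss from the per-protocol set.

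The documents give no frequency of Day 1 positives or of accepted screening positives. The power figures are therefore illustrations under assumed counts, and the simulation rests on an assumed 5% rate, a 1 SD shift and assumed correlations. The rule 5 conflict could remove more children than the Day 1 scenario if many enter on amphetamine products, but the documents do not give that share.

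**What to change.** 1. **Protocol, exclusion 30.** Replace the screening limit with *at screening or on Day 1 before randomisation*. Require the Day 1 result to be reviewed before the IXRS call. Limit the as-prescribed note to the screening visit. Have a Day 1 stimulant positive assessed with the medical monitor against the washout requirement and the re-screening provision already in Protocol 7.1 and Section 8.
2. **SAP 4.5, rule 5.** Reword so that a screening positive accepted under the note is not an important deviation. Changing exclusion 30 alone would leave this conflict in place.

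The sample is already taken, so no test is added. The cost is a short protocol amendment, one SAP edit before unblinding, and a review step on a busy classroom morning. A few children would be re-screened into a later cohort. Some of them may have completed washout, because the documents give no detection window for the assay; that is why a Day 1 positive should be assessed and not treated automatically as failed washout.
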